#### 5.3.6 Interventions

The following endpoints will be conducted on the AT population after the last active treated participant completes their 6-month follow-up; by this time, all participants still in the clinical investigation will have at least 6-months of data.

1) Intervention Post Creation to Facilitate AVF Use

Using the same definition as specified in Section 5.1.2, the number of Facilitation Interventions (On the Post-Procedure Intervention page, Date of Post Procedure Intervention is not NULL and before or on the cutoff date of the database lock, and Type of Intervention is checked as Facilitation) per PY will be estimated by Poisson regression model with only the intercept term, and the estimate and 95% CI will be provided using the Wald method. Additionally, a sensitivity analysis will be completed where the definition of facilitation interventions

is driven by the date of first successful 2-needle cannulation (Date endoAVF Successfully Used with 2 Needles for Hemodialysis on the EndoAVF Dialysis eCRF) where any intervention occurring prior to this date is counted as a facilitation intervention. Note in the event that there are multiple treatments performed during the same procedure driven by multiple reasons, each reason driving the intervention will be counted as a separate intervention.

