Intervention(s): Clinical investigation participants may require procedures that are not predetermined or planned that are performed *after* the index procedure (adjunctive procedures are those performed *during* the index procedure and second stage procedures are expected procedures that are determined a priori or at the time of the index procedure). Interventions require the completion of the Intervention eCRF. For this clinical investigation, interventions are further classified as follows and delineated by endpoint in Table 1:

- Facilitation Intervention(s): Defined as those procedures that are intended to facilitate functionality of the index AVF (i.e. those intended to support the maturation or cannulation of arterialized vein segments) and / or a procedure to address an AE related to the facilitation of index AVF functionality.
- *Maintenance Intervention(s)*: Defined as those procedures that are intended to maintain / re-establish functionality of the index AVF and / or a procedure to address an AE related to the maintenance of index AVF functionality.
- *HD Continuity Intervention(s)*: Defined as those procedures that are intended to ensure the continuity of HD (not including diagnostic studies) other than those related to the facilitation or maintenance of index AVF functionality and / or a

procedure to address an access related AE other than those related to the facilitation or maintenance of index AVF functionality. HD continuity interventions include all CVC related interventions up until the placement of a subsequent AV access following abandonment of the index AVF. HD continuity interventions exclude any intervention performed on a non-index AV access other than the placement of the non-index AV access itself.

Table 1: Eligible Interventions and Classification by Intervention Endpoint

	Facilitation I	Interventions	35	HD Continuity Interventions	
	Support of AVF Maturation	Support of AVF Cannulation	Maintenance Interventions		

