Applicable to Endpoint:	• Angioplasty / Balloon-Assisted- Maturation • Embolization of collaterals (coiling, plugging, or ligation) • Stent / stent graft • Surgical revision	Superficialization / elevation Transposition	• Angioplasty** • Banding • Embolization of collaterals (coiling, plugging, or ligation)# • Stent / stent graft • Surgical revision • Thrombectomy / thrombolysis • Treatment of aneurysm / pseudoaneurysm • Treatment of AV access infection	•Access ligation •AVF placement •AVG placement •CVC placement •Fibrin sheath removal •Treatment of infection	
Primary Effectiveness: Maintenance and / or Facilitation	Yes	Yes*	Yes	No	
Exploratory: Facilitation	Yes	Yes*	No	No	
Exploratory: Maintenance	No	No	Yes	No	
Exploratory: All Interventions	Yes	Yes*	Yes	Yes	

Excludes second stage procedures.

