#### 2) Intervention Post Creation to Maintain AVF Use

Using the same definition as specified in Section 5.1.2, the number of Maintenance Interventions (On the Post-Procedure Intervention page, Date of Post Procedure Intervention is not NULL and before or on the cutoff date of the database lock, and Type of Intervention is checked as Maintenance) per PY will be estimated by Poisson regression model with only the intercept term, and the estimate and 95% CI will be provided using the Wald method. Additionally, a sensitivity analysis will be completed where the definition of maintenance interventions is driven by the date of first successful 2-needle cannulation (Date endoAVF Successfully Used with 2 Needles for Hemodialysis on the EndoAVF Dialysis eCRF) where any intervention occurring on or after this date is counted as a maintenance intervention. Note in the event that there are multiple treatments performed during the same procedure driven by multiple reasons, each reason driving the intervention will be counted as a separate intervention.

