### 3) All Interventions Post Creation

Similarly, the number of all Interventions post creation (On the Post-Procedure Intervention page, Date of Post Procedure Intervention is not NULL and before or on the cutoff date of the database lock, and Type of Intervention is not NULL) per PY will be estimated by Poisson regression model with only the intercept term, and the estimate and 95% CI will be provided using the Wald method. Note in the event that there are multiple treatments performed during the same procedure driven by multiple reasons, each reason driving the intervention will be counted as a separate intervention. Note that for this endpoint, unlike for Facilitation and Maintenance Interventions, as HD Continuity Interventions may occur after permanent abandonment, if a participant's endoAVF has permanent abandonment the last date of available study data (including the unscheduled visit date) will be used rather than the date of permanent abandonment.

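### The date-driven facilitation and maintenance sensitivity analyses drop the intervention-type restriction, so catheter and replacement-access procedures are scored as interventions on the fistula

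*SAP*

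**What the plan says.** The main analyses in SAP 5.3.6 select by the type recorded on the Post-Procedure Intervention page. For item 1 the condition is "Type of Intervention is checked as Facilitation", and item 2 has the same condition for maintenance.

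Each item then adds a sensitivity analysis whose definition "is driven by the date of first successful 2-needle cannulation". For facilitation, "any intervention occurring prior to this date is counted as a facilitation intervention". For maintenance, "any intervention occurring on or after this date is counted as a maintenance intervention".

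Protocol 4.4 makes intervention a defined term with three classes: facilitation, maintenance and HD continuity. It says: "For this clinical investigation, interventions are further classified as follows and delineated by endpoint in Table 1". All three are recorded on the Intervention eCRF. The HD continuity column of Table 1 includes "AVF placement •AVG placement •CVC placement", together with access ligation and fibrin sheath removal. That column reads No for the primary effectiveness endpoint and for the separate facilitation and maintenance endpoints.

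The person-time for facilitation and maintenance comes from SAP 5.1.2 and ends at permanent abandonment. The only stated limit on the numerator is the database-lock cutoff. For All Interventions (item 3) the SAP extends the person-time past abandonment, "as HD Continuity Interventions may occur after permanent abandonment", and says that this differs from facilitation and maintenance.

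**The concern.** A sensitivity analysis of this kind is informative if it changes one thing. Sorting the same events by date rather than by the site's tick would show how far the split between facilitation and maintenance depends on classification, and the two rates would still add up to the primary combined rate. As written, the set of events changes as well. A catheter placed while the fistula matures becomes a facilitation intervention. A graft placed after a used fistula is lost becomes a maintenance intervention. A shift from the main analysis could then not be attributed to either cause.

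The maintenance analysis has a second problem. Protocol 4.4 keeps collecting interventions after abandonment, and "HD continuity interventions include all CVC related interventions up until the placement of a subsequent AV access following abandonment of the index AVF". Such events would enter the maintenance numerator with no matching person-time.

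**Working it through.** **1. The plan's nearest figure.** No stated figure depends on these sensitivity analyses. The closest is the power of the primary effectiveness test in SAP 2.4: 3.0 against 5 per PY, more than 100 PY, two-sided 0.05, stated as over 99%. At 100 PY the null mean is 5 × 100 = 500 events. The largest count c with P(X ≤ c | 500) ≤ 0.025 is 456. Power is P(X ≤ 456 | 300), which exceeds 99.99%. The stated figure reproduces and is untouched by this point.

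**2. Which events each rule admits.**

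| | Type restriction | Includes HD continuity | Numerator ends | Person-time ends |
|---|---|---|---|---|
| Main facilitation, maintenance | yes | no | database cutoff | abandonment |
| Date-driven sensitivity, literal | none | yes | database cutoff | abandonment |
| All Interventions | any type | yes | database cutoff | last available data |

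The second row combines the event set of the third with the person-time of the first.

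**3. One participant (dates assumed).** Catheter on day 60, first 2-needle use on day 90, angioplasty for maintenance on day 150, permanent abandonment on day 180, catheter on day 185, graft on day 240. The duration is 180 days and the SAP formula is events × 365 / days.

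- By recorded type: facilitation 0 × 365/180 = 0; maintenance 1 × 365/180 = 2.03 per PY.
- By the literal date rule: facilitation 1 × 365/180 = 2.03; maintenance 3 × 365/180 = 6.08 per PY.
- By date, restricted to facilitation and maintenance types within the duration: 0 and 2.03 per PY.

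**4. Effect on the combined rate.** Let c be the HD continuity rate per PY of the 5.1.2 person-time. The documents do not give it, so it is assumed here. If every participant's events are assigned to one side of the date, the two literal rates sum to 3.0 + c at the planning value.

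| Assumed c (per PY) | Sum (per PY) | Increase (c / 3.0) |
|---|---|---|
| 0.1 | 3.1 | 3% |
| 0.25 | 3.25 | 8% |
| 0.5 | 3.5 | 17% |
| 1.0 | 4.0 | 33% |

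**5. The post-abandonment part, maintenance only.** Assume that 5%, 10% or 20% of the 150 abandon after first use, with two later catheter or new-access procedures each. That adds 150 × 0.05 × 2 = 15, 30 or 60 events and no person-time. Over the plan's 100 PY this is +0.15, +0.30 or +0.60 per PY. Uniform 18-month accrual, a cut 6 months after the last participant and linear attrition through 20%, 40% and 60% at 6, 12 and 24 months give about 138 PY before any truncation at abandonment. On that base the additions are +0.11, +0.22 or +0.43. The abandonment shares and the procedure counts are assumptions.

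**The case against.** The strongest reply is that the narrower reading was intended. Items 1 and 2 both open by adopting the 5.1.2 definition, which is limited to facilitation and maintenance types. Table 1 excludes HD continuity from both endpoints. Item 3 sets itself apart from them because HD continuity can follow abandonment. The derived-data specification (SAP Appendix 2) is listed but not available here, and it may hold the restriction. This makes the intention plausible. It does not settle the text: the reference to 5.1.2 governs the main count, and the sensitivity sentence then says that the definition is driven by the date. Two programmers could produce different tables from it.

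Other parts of the reply stand. The SAP gives no purpose for these analyses, so testing the site's labels is an inference. Even read literally, a shift would mix relabelling with added procedures; it would not reflect added procedures alone.

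Two stronger readings are tempting. First, a reader might infer that post-abandonment events enter both analyses. In a participant who was cannulated, an event before first use cannot follow abandonment, so the mismatch is clear only for maintenance.

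Second, a reader might size the effect from the pre-market cumulative patency of 77.3% at 6 months (Protocol 2.1.2). Ignoring attrition, 150 × 0.227 is about 34 losses. One or two procedures each over 100 PY would add 0.34 to 0.68 per PY, or 11% to 23% of 3.0. The same section reports 100% functional patency through 6 months among those who used the fistula, which suggests that the early losses were in fistulas never used. Those participants have no 2-needle date: the maintenance rule cannot count their procedures, and the facilitation rule does not say what to do with them. That figure is therefore not supported.

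**Conclusion.** The point holds as a defect in the wording of two sensitivity analyses. On the literal text, HD continuity procedures are scored as facilitation or maintenance, contrary to Table 1, and the two rates need not sum to the primary combined rate. The maintenance analysis can also count procedures dated after its person-time has ended; item 3 deals with this for All Interventions only. Participants who never reach 2-needle use are not assigned by either rule.

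The size is unknown. The range of 3.1 to 4.0 per PY rests on an assumed HD continuity rate of 0.1 to 1.0 per PY and on every event being assigned to one side of the date.

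A reader might infer that the primary comparison with 5 per PY is inflated. It is not: SAP 5.1.2 keeps the type restriction, so the primary test, its power and the sample size are unaffected. The analyses concerned belong to exploratory endpoints, which Protocol 7.6 says need not be reported. The added procedures would raise the rates and so work against the device. The priority is low.

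**What to change.** In SAP 5.3.6, items 1 and 2, restrict the sensitivity count to interventions whose recorded type is facilitation and/or maintenance and whose date falls within the participant's 5.1.2 duration. Then split them: before the first successful 2-needle date is facilitation, on or after it is maintenance. Add that, for a participant with no 2-needle date, all such interventions are classed as facilitation, since none came after first use. The two rates then sum to the primary combined rate, provided that no facilitation or maintenance intervention is dated after abandonment.

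The cost is a sentence in each item, the rule for participants with no 2-needle date, and a check that Appendix 2 matches. No new data are needed.

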#### 2) Intervention Post Creation to Maintain AVF Use

Using the same definition as specified in Section 5.1.2, the number of Maintenance Interventions (On the Post-Procedure Intervention page, Date of Post Procedure Intervention is not NULL and before or on the cutoff date of the database lock, and Type of Intervention is checked as Maintenance) per PY will be estimated by Poisson regression model with only the intercept term, and the estimate and 95% CI will be provided using the Wald method. Additionally, a sensitivity analysis will be completed where the definition of maintenance interventions is driven by the date of first successful 2-needle cannulation (Date endoAVF Successfully Used with 2 Needles for Hemodialysis on the EndoAVF Dialysis eCRF) where any intervention occurring on or after this date is counted as a maintenance intervention. Note in the event that there are multiple treatments performed during the same procedure driven by multiple reasons, each reason driving the intervention will be counted as a separate intervention.

### 3) All Interventions Post Creation

Similarly, the number of all Interventions post creation (On the Post-Procedure Intervention page, Date of Post Procedure Intervention is not NULL and before or on the cutoff date of the database lock, and Type of Intervention is not NULL) per PY will be estimated by Poisson regression model with only the intercept term, and the estimate and 95% CI will be provided using the Wald method. Note in the event that there are multiple treatments performed during the same procedure driven by multiple reasons, each reason driving the intervention will be counted as a separate intervention. Note that for this endpoint, unlike for Facilitation and Maintenance Interventions, as HD Continuity Interventions may occur after permanent abandonment, if a participant's endoAVF has permanent abandonment the last date of available study data (including the unscheduled visit date) will be used rather than the date of permanent abandonment.

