4.4 Applicable Endpoint Definitions

Access Abandonment (permanent abandonment) is defined as the point at which the access can no longer be used for one or two needle prescribed HD as it may be unable to provide adequate flows and / or is deemed unsafe for the participant, and the associated problem cannot be corrected by any further intervention, including medical, surgical, or endovascular interventions or rest.^{8,19} Participants with an abandoned index AVF will continue with follow-up through 24-months and data will be collected on safety and interventions.

A HD AV access is not considered abandoned:

- If the participant discontinues use of the AV access due to kidney transplant, initiation of PD, or participant preference.
- During the maturation period or while waiting for a second stage procedure unless the principal investigator (PI) determines the participant requires and they then receive an alternative HD vascular access.

- During planned interventions, including transposition.
- If all reasonable efforts have not been attempted (and documented) to improve the condition of the access for it to be used.

A discontinuation of use of the clinical investigation AVF for any reason that does not meet this definition of access abandonment will be considered a temporary interruption.

Access Circuit Censoring Events include participant transfer to PD, kidney transplantation or the event of a participants premature discontinuation in the investigation due to withdrawn consent, withdrawal by PI, Lost to Follow-Up (LTF), or participant death (refer to Section 6.5 for definitions).

Adjunctive Procedure(s): Procedure(s) completed during the index procedure (prior to leaving the procedure room) as part of Standard-of-Care (SOC) procedures. These may include procedures to facilitate maturation and / or cannulation of the AVF, procedures to maintain use of the AVF, procedures to ensure HD continuity, as well as procedures to address AFs.

Second Stage Procedure(s): Facilitation Interventions (as defined below) intended to support the cannulation of arterialized vein segments that are determined to be needed a priori to or at the time of the index procedure (i.e. pre-planned facilitation interventions intended to support cannulation). Second stage procedures will not count against the intervention or patency endpoints and will require completion of the Second Stage Procedures eCRF.

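### The exploratory All Interventions Post Creation rate keeps adding person-time after a replacement AV access is placed, when few interventions can still count; report it split at that date as well

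*SAP*

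**What the plan says.** SAP 5.3.6(3) counts every typed post-procedure intervention up to the cutoff ("and Type of Intervention is not NULL"). It departs from the person-time rule of the other intervention rates. For the primary, facilitation and maintenance rates, time stops at permanent abandonment (SAP 5.1.2, 5.3.6(1) and (2)). Here, "if a participant's endoAVF has permanent abandonment the last date of available study data (including the unscheduled visit date) will be used". The reason given is "as HD Continuity Interventions may occur after permanent abandonment".

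Protocol 4.4 limits what an HD continuity intervention is. On catheters: "HD continuity interventions include all CVC related interventions up until the placement of a subsequent AV access following abandonment of the index AVF". On other accesses: "HD continuity interventions exclude any intervention performed on a non-index AV access other than the placement of the non-index AV access itself". The category also covers a "procedure to address an access related AE other than those related to the facilitation or maintenance of index AVF functionality". Abandonment does not end follow-up: "Participants with an abandoned index AVF will continue with follow-up through 24-months and data will be collected on safety and interventions".

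All Interventions After First Use, SAP 5.3.6(4), takes its definition from item (3) and only moves the start to first successful use. Neither document ends or splits person-time when the replacement access is placed.

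**The concern.** The SAP's reason for going past abandonment is sound until a replacement access is placed. In that interval catheter work is countable and the placement itself is still to come. After placement the reason largely lapses, but the denominator runs on, for some participants towards 24 months. That later time is nearly free of events because of a counting rule, not because little was done to the patient. Work on the new access and any further catheter procedures are simply not counted.

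This rate is meant to add replacement accesses and catheters to the facilitation and maintenance burden. A reader would take it as interventions per year of living with this fistula and its consequences. Time in which most interventions are out of scope pulls it down, in the device's favour.

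**Working it through.** **The plan's own figure.** Neither document gives a figure for this endpoint. The nearest is the primary effectiveness calculation (Protocol 7.3): more than 100 PY and over 99% power for 3.0 against 5/PY at two-sided 0.05. With 100 PY, the exact Poisson test (lower tail 0.025, mean 500) rejects at 456 or fewer events. With mean 300, the power is above 99.9%. The stated figure is reproduced.

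**What can still count after replacement (Protocol 4.4 and Table 1).**

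| Class | After a replacement access is placed |
|---|---|
| Facilitation, maintenance | Concern the index AVF, which is abandoned: closed |
| Catheter interventions | Stop at placement: closed |
| Work on the new access | Excluded: closed |
| Further AVF or AVG placement | Open |
| Index access ligation; access-related AE or infection procedures | Open, outside the new access |

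So nearly all classes close, but not all of them.

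**Inputs.** From the documents: 150 treated participants; 18-month enrolment (Protocol 3); attrition of 20%, 40% and 60% at 6, 12 and 24 months (7.3); prior 6-month cumulative patency of 77.3% (2.1.2), so 1 − 0.773 = 22.7% lost; 3.0/PY (7.3), which is the plan's assumption for facilitation plus maintenance and only illustrative here. Assumed: uniform accrual, straight-line retention between the stated points, abandonment independent of attrition and confined to the first 6 months, and a lag of 1 or 3 months to replacement.

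**Person-time.** Expected PY per participant are 0.45 by 0.5 years, 0.45 + 0.35 = 0.80 by 1 year, and 0.80 + 0.50 = 1.30 by 2 years. At the 6-month report, potential follow-up is uniform from 0.5 to 2 years. Averaging over it gives about 0.92 PY per participant, or 138.5 PY for 150 on a daily grid. This agrees with the stated figure of more than 100.

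**Share after replacement.** The share s is the PY after replacement divided by all PY. If only a fraction f of abandoned participants is replaced, the share is f × s.

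**Reported rate.** Reported rate = (rate before replacement) × (1 − share) + (rate after replacement) × share. With no countable events after replacement:

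| Lag | Replaced | PY after replacement | Share | 3.0/PY reported as |
|---|---|---|---|---|
| 1 month | all | 21.3 of 138.5 | 15.4% | 3.0 × 0.846 = 2.54 |
| 3 months | all | 16.6 of 138.5 | 12.0% | 3.0 × 0.880 = 2.64 |
| 1 month | half | 10.65 of 138.5 | 7.7% | 3.0 × 0.923 = 2.77 |
| 3 months | half | 8.3 of 138.5 | 6.0% | 3.0 × 0.940 = 2.82 |

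**Sensitivity.**
- In the 3-month, all-replaced case, allowing 0.2 or 0.5 countable events/PY after replacement gives 2.66 or 2.70 instead of 2.64.
- With all replaced, abandonment from half the prior level up to a constant hazard, and a lag of 1 to 6 months, the share runs from 3.8% to 21.7%.

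**Item (4).** Participants whose fistula is abandoned before first use contribute no time to After First Use. Protocol 2.1.2 reports 100% functional patency through 6 months among those who used the fistula. On that evidence the early losses behind the 22.7% were of fistulas not yet in use, so item (4) should be little affected early on.

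**The case against.** The best defence is that this is a deliberate and reasoned choice. Counted interventions per year of follow-up since creation is a coherent quantity, and the rate up to replacement is a different quantity, not the one true rate. That stands. It is why the planned rate should be kept and a split added. It does not remove the difficulty in reading the planned rate, because Protocol 4.4 puts most later access work out of scope.

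Several stronger readings are tempting and are not supported:

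- **That 12–15% is the expected dilution.** It requires every abandoned participant to receive a replacement AV access. Protocol 4.5.2 says the device may serve patients who are not candidates for surgical fistulas, and 4.3 treats the ability to receive another access in the same arm as an open endpoint. Participants left on a catheter remain at risk, and their time belongs in the denominator.
- **That more early failure must lower the reported rate.** Each failure can also add a catheter placement, a new access or a ligation to the numerator. The net effect is not shown.
- **That this is the only view of failed-fistula burden.** SAP 5.3.6 also gives intervention totals and counts by time point, which no denominator affects. Catheter use, cumulative patency, access continuity and abandonment are reported separately.
- **That person-time should simply end at replacement.** This would drop a second access placement, an index ligation or an access-AE procedure, all of which Protocol 4.3 and 4.4 still count.

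**Conclusion.** The mismatch between numerator and denominator is in the text of SAP 5.3.6(3) and Protocol 4.4. It lowers the rate whenever countable events are rarer after replacement than before, which the counting rule makes likely. At the 6-month report the share of person-time concerned is about 12–15% if all abandoned participants are replaced and about 6–8% if half are. An illustrative 3.0/PY becomes about 2.5–2.6 or about 2.8. These sizes rest on the earlier studies' patency (whose abandonment definition the documents do not give), the assumed lag and the assumed accrual shape. The direction does not depend on them.

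Item (4) inherits the wording, probably with little effect early on. A reader might infer that the effectiveness conclusion is at risk. It is not: the primary, facilitation and maintenance rates stop at abandonment. This endpoint is exploratory and untested, and under Protocol 7.6 it need not be reported at all. The point is minor and concerns interpretation.

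**What to change.** In SAP 5.3.6(3), and by inheritance (4), keep the planned rate and add the same rate split at the date the first subsequent AV access is placed after permanent abandonment:

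- events and person-time up to and including that placement, or up to the last study data if none is placed;
- events and person-time after it.

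State that the rate up to replacement is the one to read as the intervention burden of the index access. The split also helps with data quality. The SAP's numerator rule sets no limit at replacement, so it relies on sites typing records according to Protocol 4.4. Misclassified later procedures would show up in the second part.

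The data should already be there: the Post-Procedure Intervention page holds the intervention date (5.3.6) and the new-access question (5.3.14). The cost is one extra table row and a somewhat higher rate before replacement shown beside the planned one. No countable event is lost.
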